6.1 Experimental Procedure

Before the experiment starts, participants will visit the lab for familiarization with the 'Chairless Chair' and familiarization with the three manual materials handling tasks. They will perform the simulated assembly tasks for about 30 to 45 minutes, of which 15 to 30 minutes while wearing the exoskeleton (3.8 kg) in the different positions. During this first visit, the subjects will also complete the form with general information (Attachment 1), the form with in-/exclusion criteria (Attachment 2) and will be explained in a standardized way about how to report and judge subjective feelings of discomfort (Attachment 3). After familiarization, participants will visit the laboratory a second time during which they will perform the seven experimental conditions (exoskeleton [3], working height [3]) in a preset balanced randomized order (using a Williams Design). Before starting with the true experiment, participants will first be equipped with the measurement devices. After the preparations, participants will perform each experimental condition for ~ 20 min followed by 3-min rest breaks. During the rest break the participant will first walk around and then sit down with wearing the exoskeleton.

After finishing the experimental conditions, subjects will perform 11 trials on the force plate. Two trials will be performed while the subject is wearing the exoskeleton and is standing (1) with only his feet on the force platform while the feet of the 'Chairless Chair' are off the force platform. The trials will be recorded while in low seating and in high seating when wearing the exoskeleton and performing one work cycle in optimal height. These trials should provide insight into the body weight distribution over the own feet and the exoskeleton. Nine other trials will be performed to provide insight into the center of pressure's behavior when performing tasks in different lateral workspaces. The nine trials will include three different positions (unsupported standing, supported high seating, supported low seating) and three different frontal-lateral workspaces (narrow in a range of 120° ,

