7.3 Muscular Stress and Strain

During standing work, evaluation of the exoskeleton also includes assessing the level and development of muscle activity in selected muscles. Furthermore, it might also be interesting to investigate whether wearing or not wearing the exoskeleton is associated with any manifestations of muscle fatigue. Activity of selective muscles at the legs, back, and shoulders will be recorded. In the lower leg, the Gastrocnemius Medialis is involved in knee bending. In the upper leg, the Vastus Lateralis contributes to standing by supporting the knee and hip. At the lower back, the Erector Spinae Lumbalis helps holding up the spine. At the shoulder region, the Trapezius Descendens is one of the prone muscles during manual materials handling and is responsible for scapular movements and supports arm movements.

Activity of the muscles will be tracked continuously during the experiment using surface electromyography (EMG). This method uses recording electrodes (42×24 mm, Kendall™ H93SG ECG Electrodes, Covidien, Zaltbommel, the Netherlands) that are attached to the skin's surface overlaying the muscle of interest with an inter electrode distance (IED) of 25 mm. The differential signal (bipolar derivation) of two electrodes placed over one muscle belly, recorded by an amplifier (PS12, THUMEDI® GmbH & Co. KG, Thum-Jahnaback, Germany), gives a firm estimation of that muscle's electrical activity in microvolts (µV). This electrical activity pattern enables us to estimate the magnitude of the muscle activity (amplitude) and the overall firing frequency of the muscle (power frequency). The amplitude can be calculated by the overall root-mean-square (RMS) of the power spectrum of the EMG signal. The median power frequency (MPF) can be calculated from the power spectral density of the EMG signal by calculating the median.

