7.7 Participant Evaluation

When the participants have finished the experiment, we will provide them with a short questionnaire to report their opinion about using the exoskeleton for the various experimental conditions. This will provide us information about the acceptance of the worker regarding the use of the 'Chairless Chair'. The questionnaire will include items on feasibility, comfort, and usability (Attachment 6).

8 Statistical Analysis

When all data are collected, we will have a number of dependent variables as listed in Table 3. Each of these parameters will provide a(n) (average) value per condition, resulting in four values. For the continuous measurements, i.e. posturography, muscle strain, and work performance, we will average the values over each of the seven conditions. For the discontinuous measurements, i.e. subjective discomfort ratings, we will calculate the difference value of the pre- and post-condition measurements. Participant evaluations will not be tested but only discussed narrative.

Table 3. Summary of the model components that will be included in the statistical analyses.

Model component	Method / Name	Parameter
Dependent variable	Posturography	Center of Pressure (COP) Joint angles
	Muscle strain	Amplitude (ARV) Median power frequency (MdPF)
	Work performance	Error rate Timing error
	Subjective assessment	Rating of perceived discomfort (Borg RPE)
Within-subject factor	Working postures	Without, with (high), with (low) exoskeleton
	Working height	High, medium, low
	Working distance	Optimal, too far I, too far II
Between-subject factor	Group	Body height (S/M/L)

The current study has a repeated measures design including three within-subject factors (*exoskeleton*, *working height*, and *working distance*). If we have enough participants, we could also include a between-subject factor (*group*, based on body height), or another post-hoc identified discriminator. We will use a linear mixed effects model to perform the statistical analyses of all dependent variables (Table 3) using SPSS (IBM SPSS Statistics 23.0). This model allows observations to be not independent, because it adds a *random effect* for subject, i.e. modeled by assuming different *random intercepts* for each subject. This model also allows including both repeated measures, i.e. different conditions (within-subject factor: *working height*, *working posture*, *working distance*), and comparing independent groups of participants (between-subject factor: *group*).

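### Section 8 averages EMG over each condition, so change during a condition cannot be separated from a posture-related level difference, and the development of muscle activity is not analysed

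*Combined protocol and SAP*

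**What the plan says.** Section 7.3 states that "evaluation of the exoskeleton also includes assessing the level and development of muscle activity in selected muscles". It adds, more tentatively, that "it might also be interesting to investigate whether wearing or not wearing the exoskeleton is associated with any manifestations of muscle fatigue". EMG is recorded continuously for this purpose, and Table 3 lists EMG amplitude and MdPF as the two muscle-strain parameters.

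Section 6.1 sets the exposure: "participants will perform each experimental condition for ~ 20 min followed by 3-min rest breaks".

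Section 8 then fixes the summary: "For the continuous measurements, i.e. posturography, muscle strain, and work performance, we will average the values over each of the seven conditions". The mixed model contains posture, working height, working distance and possibly body-height group, with a random intercept per subject. It has no term for time within a condition. For discomfort ratings, by contrast, the same paragraph plans a change score: "we will calculate the difference value of the pre- and post-condition measurements".

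Section 7.4 describes reference contractions before the experiment only. They express muscle activity as a percentage of a reference contraction. No repeat contraction during or after a condition is described.

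**The concern.** Development means change over time, and a mean over the whole condition discards the time course. What remains for MdPF is one number that mixes where the signal started with how far it moved.

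The starting level may well differ between standing, high seating and low seating for reasons other than fatigue. Knee angle, muscle length and contraction level change with posture, most plainly for the two leg muscles. The subject intercept removes a man's overall level but not a posture-specific offset. The pre-experiment reference contraction gives no baseline within a condition.

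Two things are at stake. A stated target goes unanalysed although the data for it are collected. And if anyone reads a lower mean MdPF as more fatigue, a level offset could hide or reverse the answer. Section 5.5 also says the study should supply the basis for sizing follow-up projects; condition means give no variance for within-condition change, so they could not size a follow-up built on it.

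**Working it through.** The plan gives no figure to reproduce here, so the check is of what the stated summary can recover.

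**Inputs from the documents.** Condition length about 20 min (Section 6.1); work cycle about 80 s (Section 6.2); three working distances inside each condition (Section 5.1). Cycles per condition: 20 × 60 / 80 = 15, or 15 / 3 = 5 per distance if the distances take equal time.

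**Assumed inputs.** All MdPF levels and declines below.

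**1. Mean of a linear decline.** If MdPF starts at b and falls by a fraction d over the condition, the mean is b(1 − d/2).
- Standing: b = 70 Hz, d = 6%. Mean 70 × 0.97 = 67.9 Hz; fall 70 × 0.06 = 4.2 Hz.
- Seated: b = 70 × 0.95 = 66.5 Hz, d = 2%. Mean 66.5 × 0.99 = 65.8 Hz; fall 66.5 × 0.02 = 1.3 Hz.

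The seated condition has the lower mean, although its percentage decline is one third as large. The order reverses once the offset exceeds 1 − 0.97/0.99 = 2.0%, about half the difference in declines.

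**2. The same in Hz.** Compare a flat condition with one shifted by L that falls linearly by D. The difference in means is L − D/2; the difference in change over 20 min is −D.

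| L (Hz) | D (Hz) | Difference in means (Hz) | Difference in change (Hz) |
|---|---|---|---|
| −4 | 0 | −4 | 0 |
| −2 | 4 | −4 | −4 |
| 0 | 8 | −4 | −8 |
| +4 | 8 | 0 | −8 |

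The first three rows give the same mean contrast for no decline, a moderate decline and a large one. In the fourth, an 8 Hz decline disappears. The change separates all of them except rows three and four, which have the same decline.

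**3. Other shapes.** The factor of one half belongs to a linear fall. For an exponential fall with an assumed 5-min time constant, the mean carries [1 − (5/20)(1 − e⁻⁴)] / (1 − e⁻⁴) = 0.755 / 0.982 = 77% of the end-of-condition drop. The mixing remains; only the weight changes.

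**4. Whether a raw slope would do.** Not safely, because it runs across three distances. Suppose distance acts differently by posture, so that the posture contrast steps by 0, s/2 and s over three equal blocks. With time centred on −10 to 10 min, the covariance with time is (s/20) × (100 − 11.1)/2 = 2.22s and the variance of time is 400/12 = 33.3. The spurious 20-min change is 20 × 2.22s / 33.3 = 1.33s for that man. It drops out of his posture contrasts only if the distance effect is the same in every posture.

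**5. What within-block slopes cost.** Over 15 equally spaced cycles the squared deviations of time sum to 280; within three blocks of 5 they sum to 3 × 10 = 30. With independent errors between cycles (an assumption), the pooled within-block slope has a standard error √(280/30) = 3.1 times that of the raw slope.

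**The case against.** A reader might infer that MdPF is the trial's fatigue measure and that averaging leaves the trial unable to answer its fatigue question. The documents do not support that. Section 7.3 describes power frequency as reflecting overall muscle firing frequency and nowhere calls it a fatigue index. No passage says a lower mean will be read as more fatigue. Fatigue is raised only as something of possible interest, the objectives in Section 3 do not mention it, and Section 5.5 calls the study a pilot.

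Nor does a mean hide change completely: it keeps half of a linear fall and more of a front-loaded one. A reader might also infer that mean contrasts are mainly posture offset. That cannot be shown without MdPF levels or slopes, and the argument from knee angle is weaker for the back and shoulder muscles.

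Finally, the unit of summary may not be settled. Section 8 speaks of four values although there are seven conditions, and it lists working distance as a factor, which one mean per condition cannot support.

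All of this stands as a limit on the claim. It does not remove the mismatch. Development of muscle activity is stated without hedging in Section 7.3 and has no analysis. Means per distance would give three successive values per condition, but distance order varies between men and the model has no time or position term, so development would still go unanalysed.

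**Conclusion.** The point holds in this form: Section 8's averaging rule does not serve a target that Section 7.3 states, and it cannot separate level from change. A mean MdPF contrast, if read as fatigue, could be masked or reversed by a level offset. In the illustration an offset of about 2% is enough to reverse declines of 6% and 2%.

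The inseparability follows from algebra and needs no assumption about size. The Hz values, the percentages and the linear shape are assumptions. Whether a reversal would occur in these data is unknown. The link from MdPF to fatigue is a reasonable inference: MdPF is the only spectral EMG outcome, and fatigue is raised in the same section. It remains an inference, and the fatigue question is exploratory. The change is worth making before analysis, but the planned comparisons of level do not depend on it.

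**What to change.** In Section 8 and Table 3:

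- Keep the condition means of EMG amplitude and MdPF, labelled as level outcomes.
- Add, for each man, muscle and condition, a within-condition change in MdPF and in amplitude over the roughly 15 work cycles. State in advance how the two are read together, for example that only falling MdPF with stable or rising amplitude counts as a sign of fatigue.
- Do not use a raw slope or a last-minus-first difference across distances. Estimate the change within distance blocks, or fit a cycle-level mixed model with elapsed time, posture-by-time, distance and posture-by-distance terms. The cycle-level model can use the balance of distance orders across men and so should lose less precision than within-block slopes. It needs random terms for subject-by-condition as well as subject, because cycles within a condition are not independent.
- Confirm in Attachment 8 how distance orders are assigned, and reconcile the four values with the seven conditions and the three distances.
- Label fatigue results exploratory.

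The cost is SAP wording and extra processing of signals already recorded, with no added burden for participants. Change estimates are noisier than means, so intervals will be wider, and the distance adjustment costs further precision: up to about threefold in standard error for within-block slopes under the assumption above.

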Since 2014, Audi has several passive exoskeletons to use in their production lines and factories in Southern Germany, where employees perform different types of assembly work while standing (Feigl 2015; Karius 2015; Stirnemann 2015). The passive exoskeleton, the 'Chairless Chair', provides support for the lower extremities. The system is developed by the Swiss company Noonee (Saameli 2014). The 'Chairless Chair' offers the potential for a reduction of awkward body postures, even in restricted spatial conditions at standing workplaces. It is unclear which physiological and

biomechanical loads are influenced by the 'Chairless Chair' exoskeleton and how. Furthermore, it is not clear whether participants of all body heights will experience the same beneficial effects, if any, when wearing the system.

3 Objectives

This research proposal aims to provide a sophisticated study design in which participants simulate assembly work related to that performed in the Audi factories. With measurements of several physiological and biomechanical parameters, work-physiological-biomechanical analyses will be performed to investigate the influence of wearing the exoskeleton during assembly tasks. The participants included will be grouped according to their body height, enabling us to investigate whether body height influences the effectiveness of wearing the exoskeleton.

4 Timetable

The project consists of four phases (Table 1). First, the study design and measurements need to be prepared, which will take approximately three months. Participants will be recruited during three months and the measurements will take up to three months. The data analysis, evaluation, writing and publication will be spread over five months. The four phases will be performed with some overlap with a total length of the study of about ten months.

Table 1. The timetable for the proposed study that will be completed early 2018.

5 Study Design and Study Population

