Joint motion will be recorded using gravimetric position sensors (THUMEDI, Thum-Jahnsbach, Germany) which have a resolution of 0.1° and 125 ms in time, and a maximum static error of 0.5°. The sensors will be attached to the lumbar spine at the third lumbar vertebra (L3), the thoracic spine at the third thoracic vertebra (T3), and at the forehead. After calibration, each sensor measures its inclination angle with respect to the absolute perpendicular (gravitational axis) in the anterior-posterior (flexion) and medio-lateral (lateral flexion) directions. The difference between the flexion angles of the sensors at L3 and T3 results in the curvature of the spinal column; the difference between the flexion angles of the sensors at T3 and the forehead results in the neck flexion/extension angle.

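### Section 8 reduces joint angles to one mean per condition, which shows sustained shifts in flexion but not how often or how far participants leave neutral posture

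*Combined protocol and SAP*

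**What the plan says.** - **What is recorded.** Section 7.2 places sensors at L3, T3 and the forehead, where "each sensor measures its inclination angle with respect to the absolute perpendicular (gravitational axis) in the anterior-posterior (flexion) and medio-lateral (lateral flexion) directions". Two derived angles follow, both from the flexion axis. For the spine, "The difference between the flexion angles of the sensors at L3 and T3 results in the curvature of the spinal column"; the T3-to-forehead difference "results in the neck flexion/extension angle". Section 7.4 sets the upright reference posture as zero.
- **What is analysed.** Under posturography, Table 3 in Section 8 lists only "Center of Pressure (COP) Joint angles". The rule for reducing the recordings is "For the continuous measurements, i.e. posturography, muscle strain, and work performance, we will average the values over each of the seven conditions". The sentence before it reads "Each of these parameters will provide a(n) (average) value per condition, resulting in four values", a count that does not match seven conditions.
- **Why posture is of interest.** Section 2 says the device "offers the potential for a reduction of awkward body postures", and the Abstract repeats the idea. Section 7.2 supports posturography with a cited study linking low back discomfort to fewer postural adjustments in stationary standing.
- **What is not stated.** No section gives a percentile, range, variability measure, absolute value, angle limit or time in posture for joint angles, and no sign convention is written. EMG is treated differently: it is first turned into named amplitude and frequency parameters, and those are averaged.

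**The concern.** An awkward posture is an excursion from neutral, so it lies in the tail of the angle distribution over the condition. A mean describes the centre. Two conditions can share a mean while one of them includes much more time in bent posture, and the planned model would then report no difference.

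The two motives in the documents, fewer awkward postures and enough postural adjustment, both concern how posture varies over time. A single mean per condition carries neither. At stake is whether a null or favourable joint-angle result can be read as a statement about awkward posture. Section 5.5 also describes the study as a pilot for planning later projects. It would pass on variance estimates for mean angle only, and none for a measure closer to the suggested benefit.

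**Working it through.** The documents give no figure on this point, so there is none to reproduce. The check has three parts: how much the rule condenses, what a mean can and cannot separate, and where signs could cancel.

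**Inputs from the documents:** time resolution 125 ms (Section 7.2); about 20 min per condition (Section 6.1); about 80 s per work cycle (Section 6.2); upright as zero (Section 7.4).

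**Assumptions:** normally distributed angles, with the means, SDs and limits shown. The 20° limit is an example, not a recommended threshold.

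**1. Condensation.** 20 × 60 / 0.125 = 9,600 readings per sensor axis and condition, over 20 × 60 / 80 = 15 work cycles. Section 8 reduces these to one value.

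**2. Same mean, different tail.** Share of time beyond limit L = 1 − Φ((L − m)/s).

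- m = 10°, s = 5°, L = 20°: z = 2.00, share 0.0228, or 0.0228 × 20 = 0.46 min.
- m = 10°, s = 12°, L = 20°: z = 0.833, share 0.2023, or 0.2023 × 20 = 4.05 min.

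The ratio is 0.2023 / 0.0228 = 8.9, with an identical planned outcome value. Its size depends on the assumed values:

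| Mean | Limit | SD 5° | SD 10° | SD 15° |
|---|---|---|---|---|
| 10° | 20° | 2.3% | 15.9% | 25.2% |
| 15° | 20° | 15.9% | 30.9% | 36.9% |
| 20° | 20° | 50.0% | 50.0% | 50.0% |
| 20° | 30° | 2.3% | 15.9% | 25.2% |

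Where the mean sits at the limit, spread makes no difference. Where the limit is further out, it matters a good deal.

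**3. What the mean does show.** If mean flexion falls from 20° to 10° at SD 10°, the outcome moves by 10° and time above 20° falls from 50.0% to 15.9%. A sustained shift is therefore visible.

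**4. Lateral flexion, if analysed.** For a signal centred on 0°, the signed mean is 0° at every SD. The mean absolute angle is s√(2/π), which is 4.0°, 8.0° and 12.0° at SD 5°, 10° and 15°. Time beyond ±10° is 4.6%, 31.7% and 50.5%.

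**5. Flexion against extension.** Mean absolute angle = s√(2/π)·exp(−m²/2s²) + m(1 − 2Φ(−m/s)). The shortfall of the signed mean is 1 − m divided by that quantity:

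| Mean | SD 5° | SD 10° | SD 15° |
|---|---|---|---|
| 15° | 0.0% | 3.8% | 14.3% |
| 5° | 14.3% | 44.2% | 60.4% |
| 0° | 100% | 100% | 100% |

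Cancellation matters only where the angle often crosses zero.

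**6. Whether a percentile separates the cases in step 2.** 90th percentile = m + 1.2816s: 10 + 6.4 = 16.4° at SD 5°, against 10 + 15.4 = 25.4° at SD 12°. It does.

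**The case against.** A reader might infer that the device's effect on posture cannot be seen at all, or that opposite signs cancel throughout. The documents do not support either reading.

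- **Sustained shifts would show.** The design changes working position, height (−10% and +10%) and distance (+15% and +30%). These plausibly move average posture, and step 3 shows that a mean detects this.
- **Left/right cancellation is not shown for the main tasks.** In the seven conditions the work is on one triangle placed in front of the participant. Moving a weight from side to side is described only for the force-plate trials afterwards, which are not among the conditions averaged. Lateral flexion is recorded but is not a derived outcome: the Abstract names back and neck curvature, which Section 7.2 builds from flexion angles.
- **Flexion/extension cancellation is possible, not established.** No section describes neck extension during the work. With work in front of the body, flexion may stay mostly on one side of zero, where little is lost.
- **Awkward posture is a potential, not a promised endpoint.** The objective in Section 3 is the influence of wearing the device, and no primary outcome is designated.
- **The illustrative SDs are assumed.** Nothing in the documents says that conditions sharing one paced work cycle would differ in spread as much as 5° against 12°.
- **The loss is not permanent.** Participant data are to be stored for ten years after publication, so other summaries could be computed later.

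All six points stand as limits on the claim. None makes the mean a measure of excursions, because the argument in step 2 needs no sign cancellation. Summaries added later would not be pre-specified. Working distance is a model factor in Table 3, so means per distance may be intended, but Section 8 does not say so, and such means would still describe only the centre.

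**Conclusion.** The point holds in a limited form. Section 8 sets a rule, one mean per condition, that captures sustained change in joint angle and discards the tail and the spread. Those are the features closest to the potential benefit in Section 2 and to the rationale in Section 7.2. Under assumed normal angles with mean 10° and an example limit of 20°, the same outcome value is compatible with 2.3% or 20.2% of time beyond the limit. The actual difference between conditions cannot be known from the documents and may be smaller.

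The angles appear to be signed, because upright is zero and the neck scale runs from flexion to extension, but this is an inference. Cancellation is a conditional concern: near-complete for lateral flexion if it is analysed as a signed mean and centred on zero, and anywhere from negligible to large for the neck depending on where its mean lies. This is an inexpensive improvement to an exploratory pilot, not a flaw that invalidates the analysis.

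**What to change.** In Section 8 and Table 3:

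1. Name the analysed angles (spinal curvature from L3 and T3; neck angle from T3 and forehead) and state the sign convention for each.
2. Keep the mean, or the median, as the central summary.
3. Add the 90th percentile within each condition, and within each working distance where distance is tested. For the neck, add the 10th percentile to capture extension.
4. If lateral flexion is analysed, take its absolute value before summarising.
5. Fit these in the same linear mixed model and label the added summaries exploratory.
6. Correct the stated number of values per parameter so that it agrees with the seven conditions.

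A percentile is suggested in place of time beyond a limit because the documents give no angle limit. It describes the tail; it does not count postural adjustments.

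**Cost.** Wording and a few lines of processing code, using recordings already planned. The downside is one or two extra summaries per angle, and so extra tests in a plan that already has many outcomes and states no multiplicity control. This is why the exploratory label is needed.

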5.1 Study Design

The laboratory study will include several experimental conditions, being a combination of supported seating or unsupported standing by the exoskeleton, and three different working heights. These seven combinations will be offered to the subjects in a balanced, randomized cross-over design (Latin Square Williams Design; Williams 1949). In each of these seven conditions, three manual materials handling tasks will be simulated in a fixed order but in three different frontal working distances. Because of the three working distances, we will include a multiple of the 14 orders resulting from the Williams Design, striving for a population of 42 subjects.

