7.6 Subjective Assessment

Participants will rate their overall subjective feeling of discomfort (RPD) on a 11-point numerical rating scale (McCaffery & Beebe 1989; Figure 6; Attachment 3). When participants experience a feeling of discomfort > 0, we ask them to define the body region (Kuorinka et al. 1987) which is causing this sensation.

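### The pre/post difference for discomfort fixes the slope on the pre-condition rating at 1; using that rating as a covariate would be as precise or more so, by an amount the documents do not settle

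*Combined protocol and SAP*

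**What the plan says.** Section 7.6 has the participant give one overall discomfort score "on a 11-point numerical rating scale". Section 8 turns the scores around each condition into a single value: "we will calculate the difference value of the pre- and post-condition measurements". That value goes into the same random-intercept linear mixed model as every other outcome.

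Table 3, captioned "Summary of the model components that will be included in the statistical analyses", lists dependent variables, three within-subject factors and one between-subject factor. It lists no covariate and no period term. The between-subject factor, body-height group, is conditional: "If we have enough participants, we could also include a between-subject factor".

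On the design, Section 5.1 says "These seven combinations will be offered to the subjects in a balanced, randomized cross-over design". Section 6.1 has each condition last about 20 minutes, "followed by 3-min rest breaks".

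Section 8 gives no reason for choosing the difference. No SD, pre/post correlation, significance level or power is stated anywhere, and Section 5.5 describes the study as a pilot.

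A separate matter to reconcile: Table 3 labels this outcome Borg RPE, whereas Section 7.6 describes an 11-point numerical rating scale.

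**The concern.** Subtracting the pre-rating is the same as including it in the model with a coefficient of exactly 1. Here the pre-rating is a single score on a short bounded scale, taken once per condition. For all but the first condition it comes at most a few minutes after the previous one ended. Measurement error, rounding and fading residue would each tend to pull the true coefficient below 1. If it is below 1, the difference brings more of the pre-rating's noise into the outcome than it removes.

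The random intercept does not cure this. It removes stable differences between men, not the variation of one man's pre-ratings from condition to condition.

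At stake is the precision of the posture and working-height contrasts for the only subjective outcome that is to be tested, since the participant evaluation is only discussed narratively. There is also a knock-on effect. Section 5.5 wants this pilot to support a sample-size calculation for later projects, and a residual SD taken from the noisier analysis would carry over into that calculation.

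**Working it through.** **The plan's own figure.** Section 5.1 reaches its target from the design: 14 Williams orders × 3 = 42 men. Section 5.5 gives a minimum of 21, which matches 7 conditions × 3 distances. Both reproduce. Neither comes from a power calculation, so there is no stated precision to reproduce. The orders printed in Figure 1B are balanced: each condition appears twice in each position, and all 7 × 6 = 42 ordered pairs of distinct conditions occur, each twice.

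**Inputs.** From the documents: 7 conditions per man, 42 men (minimum 21), one pre- and one post-rating per condition, no covariate. Assumed, because not given: the within-man correlation *r* between pre- and post-rating, and *k* = SD(pre)/SD(post). Both are taken after removing man, period and condition effects, and the post-rating SD is set to 1.

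**Formulas.**
- Difference: variance = 1 + k² − 2rk
- Pre-rating as covariate: variance = 1 − r²
- Excess of the difference: (1 + k² − 2rk) − (1 − r²) = (k − r)², which is never negative

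The post-on-pre slope is r/k, so the excess is zero when the slope is 1. If the pre-rating does not vary at all, the two analyses coincide. If the slope lies between 0 and 1, then r lies between 0 and k and the excess is at most k². At k = 0.25 that is at most 0.0625, so little is lost when pre-ratings barely vary.

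**Equal SDs (k = 1).** The ratio simplifies to (1 − r²)/(2(1 − r)) = (1 + r)/2. The minimum detectable difference (MDD) for a pairwise contrast is (1.96 + 0.84) × √(2 × variance/42), in within-man SDs of the post-rating. Two-sided 5% and 80% power are assumptions.

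| r | Difference | Covariate | Ratio | 42 × ratio, rounded up | MDD, difference | MDD, covariate |
|---|---|---|---|---|---|---|
| 0.3 | 1.40 | 0.91 | 0.65 | 28 | 0.72 | 0.58 |
| 0.5 | 1.00 | 0.75 | 0.75 | 32 | 0.61 | 0.53 |
| 0.7 | 0.60 | 0.51 | 0.85 | 36 | 0.47 | 0.44 |
| 0.9 | 0.20 | 0.19 | 0.95 | 40 | 0.27 | 0.27 |

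The fifth column is the number of men with whom the covariate analysis would match the 42-man difference analysis. At r = 0.3 the difference (1.40) is noisier even than the post-rating alone (1.00).

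**Pre-SD half of post-SD (k = 0.5).** The difference variance is 1.25 − r.

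| r | Slope r/k | Difference | Covariate | Ratio |
|---|---|---|---|---|
| 0.3 | 0.6 | 0.95 | 0.91 | 0.96 |
| 0.5 | 1.0 | 0.75 | 0.75 | 1.00 |
| 0.7 | 1.4 | 0.55 | 0.51 | 0.93 |

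**Simulation check.** Setting: the printed orders with 42 men, normally distributed ratings, man, period and condition effects, 600 runs. The standard error of a condition contrast, difference against covariate, was 0.244 v 0.202 (r = 0.3, k = 1), 0.223 v 0.192 (r = 0.5, k = 1), 0.177 v 0.160 (r = 0.7, k = 1) and 0.187 v 0.187 (r = 0.5, k = 0.5). The first three give variance ratios of about 0.69, 0.74 and 0.82, close to the formula.

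**Cost in degrees of freedom.** 42 × 7 = 294 observations, less 42 men, 6 for period and 6 for condition, leaves 240; the covariate uses one. With 21 men it is 147 − 21 − 6 − 6 = 114.

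**The case against.** The strongest reply has four parts.

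1. *The gain may be trivial.* Section 5.3 excludes people with acute ailments or pain, and every pre-rating follows a rest or the start of the session. Many pre-ratings may sit at or near 0. That suggests k below 1, where the k = 0.5 figures show almost nothing to gain. This stands as a limit on size. It does not change the direction, because (k − r)² cannot be negative.

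2. *The covariate is not free of bias.* If the pre-rating carries residue of the previous condition, it is partly a lagged outcome, and with seven periods its within-man slope is underestimated. The man's mean pre-rating also includes later ratings that earlier conditions may have affected. Because no condition follows itself, a more uncomfortable condition tends to have slightly lower pre-ratings, so an underestimated slope shrinks contrasts a little. By the same mechanism, a slope of 1 that is too high inflates them a little. In simulations with assumed residue and a true contrast of 1.8, the covariate model gave 1.73 to 1.78 and the difference 1.80 to 1.89. In others, with integer 0–10 ratings and a true contrast of 1.0, the attenuation was about 0.01 to 0.11, and the covariate model's root mean square error was never worse than that of the difference. The caveat stands and belongs in the plan, but it does not reverse the balance.

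3. *The difference is a recognised analysis with a plain meaning*, namely how much discomfort rose during a condition. True, and a reason to keep reporting it.

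4. *This is a pilot with no precision target, and discomfort is one of several outcomes, none designated primary.* Also true; it limits the importance of the point.

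The exact rating times within the breaks cannot be read from the available text, so the amount of residue cannot be judged.

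**Conclusion.** The point holds as a modest matter of efficiency. For the posture and working-height contrasts, the planned difference is never materially more precise than covariate adjustment, and it is less precise unless the post-on-pre slope is near 1 or the pre-rating barely varies. The direction is algebra. The size rests wholly on assumed r and k: from about a third of the variance (r = 0.3, k = 1) down to nothing (r = 0.5, k = 0.5).

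Three stronger readings are tempting, and the documents do not support them:
- *That the planned analysis is biased or mistaken.* Neither analysis is clearly better on bias, and no contradiction in the plan is involved.
- *That a definite share of the sample is wasted.* The larger savings in men need equal pre and post SDs, which the documents neither state nor make likely.
- *That every discomfort contrast is affected.* Discomfort is rated before and after a condition. No separate rating per working distance is described, so there is no distance contrast to sharpen. For the optional body-height groups, which are not randomised, adjusting for the pre-rating changes the question asked rather than simply the precision.

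**What to change.** In Section 8, replace the sentence on discomfort with one to this effect: *the post-condition rating is the dependent variable; that condition's pre-rating is a covariate; condition and period are fixed effects, with a random intercept per participant; the raw difference is reported as a descriptive or sensitivity result.* Add the pre-rating and period to Table 3.

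Optionally, split the pre-rating into the man's mean and his deviation from it, so that the slope used for the contrasts is the within-man one. Keeping the difference as outcome and adding the same covariate gives identical condition contrasts; only the covariate's coefficient shifts by 1.

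State the downside beside it: one or two extra parameters, and a possible small attenuation of contrasts if pre-ratings carry residue of the preceding condition. If the body-height comparison is run, say whether it is adjusted for the pre-rating and that adjustment alters what is being compared. For the follow-up sample-size calculation, report the pre and post SDs and their within-man correlation.

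No new measurement, visit or participant is needed.
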